Attachments

ATTACHMENT B

Detailed Measure Specifications and Scoring for FECC Caregiver Survey Indicators

All are on 0-100 scale, where higher is better. Survey response items should be coded to reflect that. For dichotomous items, "no" = 0 and "yes" = 100. More specific instructions are included where applicable in Scoring Notes.

All screener items must be nonmissing for a dependent item to be scored

If items are part of a yes/no checklist, if at least one item is answered, impute "no" for skipped items in mailed surveys or "don't know" for telephone surveys (but not for items that telephone respondents refused to answer).

Otherwise, all component items must be nonmissing for a multi-item indicator to be scored.

MP=Main Provider

Indicator ID	Indicator Description	Eligible	Survey Item	Scoring notes
CARE COORDINATION SERVICES				
CC2	Caregivers should report that their child has a designated care coordinator.	Q2=1 (Child visited more than one doctor's office or used more than one kind of health care service in last 12 months)	Q3 (Someone in MP's office helped manage child's care or treatment from different doctors/providers)	
CC3	Caregivers who report that their child has a designated care coordinator (as identified in CC2) should report that they know how to access their care coordinator.	Q2=1 (Child visited more than one doctor's office or used more than one kind of health care service in last 12 months), Q3=1 (Someone in MP's office helped manage child's care or treatment from different doctors/providers)	Q6 (Knew how to contact person who helped manage child's care when you needed help or had a question)	
CC5	Caregivers who report having a designated care coordinator (as identified in CC2) and who require community services should also report that their care coordinator helped their child to obtain needed community services in the last year.	Q2=1 (Child visited more than one doctor's office or used more than one kind of health care service in last 12 months), Q3=1 (Someone in MP's office helped manage child's care or treatment from different doctors/providers), Q15=1 (Caregiver or child needed or used community services in last 12 mos)	Q16(Person in MP's office who helped manage child's care helped get community services)	

CC7	Caregivers who report having a care coordinator (as identified in CC2) should also report that their care coordinator has contacted them (via face-to-face contact, telephone, email, or written correspondence) or attempted to contact them at least once in the last 3 months.	Q2=1 (Child visited more than one doctor's office or used more than one kind of health care service in last 12 months), Q3=1 (Someone in MP's office helped manage child's care or treatment from different doctors/providers)	Q7 (In last 3 mos, person contacted you w/o you getting in touch w/them first)
CC8	Caregivers of children with complex needs who report having a care coordinator and who report that their care coordinator has contacted them in the last 3 months should also report that their care coordinator asked them about the following:	Q2=1 (Child visited more than one doctor's office or used more than one kind of health care service in last 12 months), Q3=1 (Someone in MP's office helped manage child's care or treatment from different doctors/providers), Q7=1 (In last 3 mos, care coordinator contacted you w/o you getting in touch w/them first)	Mean of CC8a and CC8b
CC8a	Caregiver concerns	Q9 (Care coordinator asked about caregiver concerns)	
CC8b	Health changes of the child	Q10 (Care coordinator asked about health changes of child)	
CC8c	Caregivers who report the following: having a designated care coordinator, having a copy of a written shared care plan for their child, and having been contacted by their care coordinator in the last 3 months should also report that their care coordinator asked them about the following: Progress towards goals documented in the patient's shared care plan	Q2=1 (Child visited more than one doctor's office or used more than one kind of health care service in last 12 months), Q3=1 (Someone in MP's office helped manage child's care or treatment from different doctors/providers), Q7=1 (In last 3 mos, care coordinator contacted you w/o you getting in	Q31 (In last 12 mos, has MP or anyone from MP's office talked w/you about progress child was making toward goals written in shared care plan) If Q31=3 (Child's shared care plan does not have written goals), score as No

		touch w/them first), Q29=1 (MP created shared care plan for child), Q30=1 (Caregiver has copy of child's shared care plan)		
CC9	Caregivers who report their child was referred to see a specialist in the last 12 months and who report having a care coordinator for their child should also report that the care coordinator contacted them to confirm they were able to get an appointment with the specialist	Q2=1 (Child visited more than one doctor's office or used more than one kind of health care service in last 12 months), Q3=1 (Someone in MP's office helped manage child's care or treatment from different doctors/providers), Q13=1 (MP told you child needed to see specialist during last 12 mos)	Q14 (Person in MP's office who helped manage child's care contacted you to make sure child got appointment to see specialist)	If Q14=3 (Did not get help managing child's care), score as No
CC10	Caregivers who report having a care coordinator should also report that their care coordinator:	Q2=1 (Child visited more than one doctor's office or used more than one kind of health care service in last 12 months), Q3=1 (Someone in MP's office helped manage child's care or treatment from different doctors/providers)	Q5 (In last 12 mos, person in MP's office who helped manage child's care...)	Give partial credit (No=0, Yes Somewhat=50, Yes Definitely=100), take mean of CC10a-c
CC10a	Was knowledgeable about their	Q5a, Q5b		Mean of rescaled Q5a and Q5b

	child's health			
CC10b	Supported the caregiver		Q5c	
CC10c	Advocated for the needs of the child	Q5d, Q5e		Mean of rescaled Q5d and Q5e
MH8	Caregivers or patients who self-identify as having a preference for conducting medical visits in a language other than English should have access to a professional medical interpreter (live or telephonic) at all visits for which an interpreter is needed.	Q39=1 (Speak language other than English at home), Q41=2 (Prefer to talk w/child's doctors in language other than English), Q44=2, 3, or 4 (Needed professional interpreter during visit to MP some, most, or all visits)	Q45 (How often was professional interpreter available when needed)	Partial credit: rescale Q45 to 0-100 Q45=1 (Never): 0 points, Q45=2 (Sometimes): 100/3 points, Q45=3 (Usually): 100*2/3 points, Q45=4 (Always): 100 points
MESSAGING				
IE2	Caregivers/patients who report receiving a written visit summary during the last 12 months from their child's MP's office should report that it contained the following elements:	Q17=1 (received written visit summary in last 12 mos)	Q18 (How often did written visit summaries include...)	Give partial credit (Never=0, Sometimes=50, Always=100), take mean of IE2a-f
IE2a	Current problem list		Q18a	
IE2b	Current medication list	Q18b (Rx), Q18c (OTC)		Mean of rescaled Q18b and Q18c
IE2c	Drug allergies		Q18d (list of "child's allergies", not drug allergies specifically)	
IE2d	Specialists involved in the child's care		Q18e	
IE2e	Planned follow-up		Q18f	
IE2f	What to do for problems related to the		Q18g	

outpatient visit

IE3	Caregivers/patients who reported ever receiving a visit summary in the last 12 months from their child's MP's office (as identified in IE2) should report that the summary:	Q17=1 (received written visit summary in last 12 mos)	Give partial credit (Never=0, Sometimes=50, Always=100), take mean of IE3a and IE3c
IE3a	Was easy to understand	Q19	
IE3c	Was useful	Q20	
IE4	Caregivers should report having been invited to join in hospital rounds during their child's last hospitalization	Q21=1 (child had overnight hospital stay in last 12 mos)	Q25 (Last time child was in hospital, invited to take part in hospital rounds)
IE5	Caregivers/patients should report receiving a written visit summary of their child's last hospitalization at the time of discharge, and they should report the summary contained the following elements:	Q21=1 (child had overnight hospital stay in last 12 mos), Q22=1 (Last time child was in hospital, got written hospital stay summary at discharge)	Q23 (Did written hospital stay summary include...) Mean of IE5a-f
IE5a	Problem list at time of discharge	Q23a	
IE5b	Medication list at time of discharge	Q23b (Rx), Q23c (OTC)	Mean of rescaled Q23b and Q23c
IE2c	Drug allergies	Q18d (list of "child's allergies", not drug allergies specifically)	
IE2d	Specialists involved in the child's care	Q18e	
IE2e	Planned follow-up	Q18f	
IE2f	What to do for problems related to the outpatient visit	Q18g	

IE3	Caregivers/patients who reported ever receiving a visit summary in the last 12 months from their child's MP's office (as identified in IE2) should report that the summary:	Q17=1 (received written visit summary in last 12 mos)	Give partial credit (Never=0, Sometimes=50, Always=100), take mean of IE3a and IE3c
IE3a	Was easy to understand	Q19	
IE3c	Was useful	Q20	
IE4	Caregivers should report having been invited to join in hospital rounds during their child's last hospitalization	Q21=1 (child had overnight hospital stay in last 12 mos)	Q25 (Last time child was in hospital, invited to take part in hospital rounds)
IE5	Caregivers/patients should report receiving a written visit summary of their child's last hospitalization at the time of discharge, and they should report the summary contained the following elements:	Q21=1 (child had overnight hospital stay in last 12 mos), Q22=1 (Last time child was in hospital, got written hospital stay summary at discharge)	Q23 (Did written hospital stay summary include...) Mean of IE5a-f
IE5a	Problem list at time of discharge	Q23a	
IE5b	Medication list at time of discharge	Q23b (Rx), Q23c (OTC)	Mean of rescaled Q23b and Q23c
IE5c	Drug allergies		Q23d (list of "child's allergies", not drug allergies specifically)
IE5d	Specialists involved in the child's care during the hospitalization		Q23e
IE5e	Planned follow-up		Q23f
IE5f	What to do for problems related to the hospitalization		Q23g
IE6	Caregivers who received a written summary of their child's hospitalization at discharge (as	Q21=1 (child had overnight hospital stay in last 12 mos), Q22=1 (Last time child was in	Q24 (Hospital stay summary easy to understand)

described in indicator IE5) should report that the information contained in the visit summary was easy to understand hospital, got written hospital stay summary at discharge)

MH3a	Caregivers should report having access to an electronic health record to look up information about their child's visits and health care.	All caregivers of children with medical complexity	Q26 (In last 12 mos, MP's office had web site or app caregiver could use between visits to look up information about child's visits and care)	If Q26=1 (Yes): 100 points If Q26=2 or 3 (No or Don't Know): 0 points
MH3b	Caregivers who report having access to an electronic health record should also report that it includes the following health information:		Q26=1 (In last 12 mos, MP's office had web site or app caregiver could use between visits to look up information about child's visits and care)	Do not score the N/A's; If no immunizations (meds), do not score MH3b1 (MH3b2); If didn't look at med list, do not score MH3b2 Take mean of MH3b1 and MH3b2
MH3b1	Immunization record		Q26=1 (In last 12 mos, MP's office had web site or app caregiver could use between visits to look up information about child's visits and care)	If Q27=3 (no immunizations in last 12 mos): do not score If Q27=1 (Yes): 100 points If Q27=2 or 4 (No or Don't Know): 0 points
MH3b2	List of child's medications		Q26=1 (In last 12 mos, MP's office had web site or app caregiver could use between visits to look up information about child's visits and care)	If Q28=3 (no meds in last 12 mos): do not score MH3b2 If Q28=1 (Yes): 100 points for MH3b2 If Q28=2 or 4 (No or Don't Know): 0 points for MH3b2

MH6	Caregivers who report their child's condition causes difficulty learning, understanding, or paying attention in class should also report that one of their child's health care providers (i.e., primary care physician, specialist physician, care coordinator, NP, nurse, social worker, etc) communicated with school staff at least once a year about the educational impacts of the child's condition.	Q35=1 (Child attended school in last 12 mos), Q36=1 (Because of health condition child has difficulty learning, understanding, or paying attention in class)	Q37 (In last 12 mos, someone from MP's office contacted staff at child's school to make sure they understood how child's condition affected ability to learn, understand, or pay attention)	If Q37=1 (Yes): 100 points If Q37=2 or 3 (No or Don't Know): 0 points
PROTOCOLS/PLANS				
SCP2	Caregivers should report that their child's primary care provider created a shared care plan for their child.	All caregivers of children with medical complexity	Q29 (MP created shared care plan for child)	Q29=1 (Yes): 100 points Q29=2 (No): 0 points
SCP4	Caregivers of children (age 15 years or older) should report that their child's main provider created a written transition plan for their child.	Q33=1 (Child age 15 or older)	Q34 (MP created transition plan for child)	Q34=1 (Yes): 100 points Q34=2 or 3 (No or Don't Know): 0 points
SCP6	Caregivers should report that their child's main provider created an emergency care plan for their child.	All caregivers of children with medical complexity	Q32 (MP created emergency care plan for child)	Q32=1 (Yes): 100 points Q32=2 (No): 0 points

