While we believe this is the strongest study design for this Aim given the available data, the lack of a control group cannot rule out other explanations for differences in outcomes over time. Therefore, we will carefully consider alternative explanations to other trends with our Patient Advisory Panel and other key experts once we obtain preliminary analytic results. We will additionally examine the potential for controls from children in other regions of Ohio for a case/control analyses. Although ACO assignment was mandatory and assigned based only on region and thus may not suffer from self-selection bias, if we are able to incorporate data from children in other regions, we will carefully examine the baseline characteristics, utilization during the pre-treatment period and risk factors between ACO and other ABD children in Ohio to ensure balance in covariates. Incorporating control data from Medicaid claims for children in states other than Ohio is not plausible, given that these data are available with a three-year lag and thus post-period analysis would not be possible during our study period.

Sub-group analysis: Although our primary goal is to estimate the effect of ACO enrollment on vulnerable ABD children overall, we will also estimate the *heterogeneity of the ACO treatment effect* in populations defined by age, race/ethnicity, gender, care coordination metrics and diagnostic group to the extent allowable by sample size. The specific subgroups will be identified in advance collaboratively with our stakeholders. This sub-analysis will control for the health status and disease progress of a patient during the 6-year period.

We will also look at the impact of specific elements of care coordination provided on a subgroup of our population using information collected in our caregiver survey and medical record review. For example, as noted above, one of our potential outcomes variables is use of the emergency department. One potential research question is whether emergency department use is lower in children whose caregivers reported receipt of an understandable visit summary after their last outpatient visit.

Data Safety, Monitoring, and Handling

Aim 1

Interview data collected from participants will be identified only by an assigned participant ID number, not by name. The data confidentiality and informed consent process will be explained by the investigator prior to the start of the interview and before the recording begins.

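### IE5 (Attachment B) is defined to include receipt of a discharge summary, but its eligibility rule removes every caregiver who received none, so the receipt half cannot be failed

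*Combined protocol and SAP*

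**What the plan says.** The IE5 row of Attachment B opens with receipt: caregivers "should report receiving a written visit summary of their child's last hospitalization at the time of discharge". It then adds that the summary should have contained six listed elements. The eligibility column for the same row reads "Q21=1 (child had overnight hospital stay in last 12 mos), Q22=1 (Last time child was in hospital, got written hospital stay summary at discharge". The scored item is "Q23 (Did written hospital stay summary include", with the score taken as the mean of IE5a to IE5f. Q22 is not itself a scored item.

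Three neighbouring indicators also use a receipt screen, but their descriptions say so. IE6 begins "Caregivers who received a written summary of their child's hospitalization at discharge (as" and uses the same two screeners as IE5. IE2 begins "Caregivers/patients who report receiving a written visit summary during the last 12 months from their child's MP's office should report that it contained", and IE3 is worded in the same way; both require "Q17=1 (received written visit summary in last 12 mos".

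The Analysis section of Aim 2 plans to report every indicator by age group, urban/rural residence and physical versus mental diagnosis, and to judge both the quality and the completeness of care coordination. It also plans to relate receipt of care coordination elements to outcomes, with receipt of a discharge summary and 30-day readmission as an example. The Sub-group analysis section of Aim 3 offers a similar illustration: "whether emergency department use is lower in children whose caregivers reported receipt of an understandable visit summary after their last outpatient visit".

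**The concern.** The description and the denominator of IE5 disagree. The description makes receipt something a caregiver should report; the eligibility rule makes receipt a condition of being counted. A hospitalised child whose caregiver got nothing in writing is the clearest failure of the indicator as described, and that child is left out.

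Two uses are affected. First, the IE5 figure would be read as performance on giving families a complete discharge summary when it measures only the content of the summaries that were given. A subgroup in which few caregivers received one could look as good as, or better than, a subgroup in which nearly all did. Second, if IE5 or IE6 scores were used as the exposure in a linked analysis of discharge-summary receipt, the natural comparator, children whose caregivers received no summary, would be absent.

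**Working it through.** **Step 1. Could another rule or indicator score non-receipt?**

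- The general scoring rules at the top of Attachment B require screeners to be nonmissing. They do not give a score of 0 when a screener is answered no.
- The rule that fills skipped checklist items with no needs at least one answered item. A non-recipient has no Q23 answers to build on, and the Q22=1 screen excludes that caregiver in any case.
- Q22 appears only as a screener, for IE5 and IE6. Q17 appears only as a screener, for IE2 and IE3. Neither is the scored item of any listed survey indicator.

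**Step 2. How does the same table treat parallel cases?**

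| Screening item | Scored in its own right | Then used as a screen for |
|---|---|---|
| Q3, has a care coordinator | CC2 | CC3 and later CC items |
| Q26, has electronic record access | MH3a (no or don't know = 0) | MH3b |
| Q29, has a shared care plan | SCP2 | CC8c |
| Q22, got a discharge summary | none | IE5, IE6 |

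Within single items, too, absence counts as failure: CC8c scores a plan without written goals as no, and CC9 scores not having had help managing care as no. IE5 departs from this pattern although its description names receipt.

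**Step 3. Size.**

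Let r = share with Q22=1 among Q21=1, and S = mean of IE5a to IE5f among recipients, assuming every recipient can be scored.

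- IE5 as specified = S.
- IE5 as described, with non-receipt scored 0 = r × S + (1 − r) × 0 = r × S.
- Overstatement = S − r × S = S × (1 − r), which is zero only if r = 1 (or S = 0).

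The documents state neither r nor S. Over an assumed range, r × S is as follows, with the overstatement in brackets:

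| S | r = 0.9 | r = 0.7 | r = 0.5 | r = 0.3 |
|---|---|---|---|---|
| 90 | 81 (9) | 63 (27) | 45 (45) | 27 (63) |
| 80 | 72 (8) | 56 (24) | 40 (40) | 24 (56) |
| 60 | 54 (6) | 42 (18) | 30 (30) | 18 (42) |

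**Step 4. Can subgroup order change?**

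Yes, if receipt differs between subgroups. Suppose group A has r = 0.4 and S = 90, and group B has r = 0.9 and S = 80 (both assumed). As specified, A leads B by 90 to 80. With non-receipt scored 0, A has 0.4 × 90 = 36 and B has 0.9 × 80 = 72.

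The plan states no figure for IE5 itself, so there is none to reproduce.

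**The case against.** The strongest defence is that Attachment B sets out the scoring of an existing, field-tested instrument. The missing-data section for the Aim 2 survey commits to the survey's scoring guide so that results match other implementations, and Aim 2 plans comparison with pilot data where appropriate. Changing IE5 would break that link. This stands as a reason to keep the guide's IE5. It is not a reason to leave non-receipt unreported: the commitment to the guide concerns missing responses, and a no to Q22 is a valid answer.

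It can also be said that scoring non-receipt as 0 on every content element is one choice among several and mixes access with content. That is fair, and it is why the receipt rate should be shown separately as well.

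A reader might go further in four ways that the documents do not support.

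- *IE2, IE3 and IE6 have the same error.* They do not. Each is worded as conditional on receipt, so its eligibility matches its description. A companion receipt rate would be an addition, not a correction.
- *The planned emergency-department analysis drops children with no summary.* The Sub-group analysis section presents this as one potential question, to be answered with information from the survey and record review. It does not define the exposure as an IE3 score, and Q17 is collected.
- *Non-receipt is measured nowhere in the study.* The 31 measures include record-review measures whose specifications are not in the text available, so the statement can be made only for the survey indicators in Attachment B.
- *The score is inflated by some particular number of points.* Any such number rests on assumed values of r and S.

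**Conclusion.** The point holds for IE5. Its description includes receipt, its eligibility rule conditions on receipt, only content is scored, and no Attachment B survey indicator captures receipt. Followed as written, the plan yields an IE5 figure that does not measure what its description states. It exceeds the figure the description implies by S × (1 − r) whenever some hospitalised children's caregivers received no summary and recipients' scores are above zero. How large this is in the study cannot be known from the documents.

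The conclusion matters beyond labelling because Aim 2 promises to assess completeness and its consistency across subgroups, and names receipt of a discharge summary as an exposure. It should be corrected before results are reported. It does not extend to IE2, IE3 or IE6 as errors.

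**What to change.** 1. Keep the scoring-guide IE5 for comparison with other users of the survey, and label it as conditional on having received a summary.
2. Report beside it, overall and by the planned subgroups: (a) the receipt rate, Q22 among Q21=1, scored 0/100; and (b) a full IE5 among Q21=1, with Q22=no scored 0.
3. In any linked analysis of receipt of a discharge or visit summary, state that non-recipients (Q22=no or Q17=no) stay in as an exposure level.
4. Leave IE2, IE3 and IE6 unchanged. A Q17 receipt rate may be added as a supplement, limited to children with a main-provider visit in the last 12 months where this can be identified. Taken among all respondents, it could count a child with no such visit as a failure.

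The cost is a short addition to the scoring text and a few lines of analysis code. Q17, Q21 and Q22 are already asked, so there is no added burden on respondents. The downside for the study team is that the full IE5 will look less favourable than the conditional one.
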